### 7.1.2 QTc Stopping Criteria

A participant who meets either bulleted criterion based on the average of triplicate ECG readings will be withdrawn from study medication.

- QTc  $>500\text{msec}$  OR Uncorrected QT  $>600\text{msec}$

- Change from baseline of QTc >60msec

For participants with underlying bundle branch block, follow the discontinuation criteria listed in **Table 7-1**.

**Table 7-1: Bundle Branch Block discontinuation criteria**

Baseline QTc with Bundle Branch Block	Discontinuation QTc threshold with Bundle Branch Block
< 450msec	> 500msec
450 to 480msec	≥ 530msec

If a clinically significant finding is identified (including, but not limited to, changes from baseline in QTcF after enrollment), the investigator, study physician, or medically qualified designee will determine if the participant can continue in the study and if any change in participant management is needed. This review of the ECG printed at the time of collection must be documented. Any new clinically relevant finding should be reported as an AE.

See the Schedules of Activities for Part A ([Table 1-4](#)), Part A1 ([Table 1-5](#) and [Table 1-6](#)), Part B ([Table 1-7](#)), and Part C ([Table 1-8](#)) for data to be collected at the time of treatment discontinuation and follow-up and for any further evaluations that need to be completed.

### 7.1.3 Other criteria for discontinuation of study medication

Participants must discontinue study treatment if they experience any of the following:

1. There is confirmation of a pregnancy during the study, as evidenced by a positive pregnancy test.
2. The participant experiences unacceptable toxicity.
  - For information on dose delays due to drug-related toxicity, see Section [6.6.1](#) (Part A and Part A1), Section [6.6.2](#) (Part B), and Section [6.6.3](#) (Part C). Participants will discontinue treatment, unless, in the opinion of the investigator, they are experiencing clinical benefit and it is in their best interest to continue treatment. For these participants, treatment may continue at a reduced dose at the discretion of the investigator and Sponsor.
3. The participant has documented evidence of progressive disease.
  - Participants with progressive disease before the end of Cycle 1 may be discontinued from study medication at the discretion of the investigator. Participants with progressive disease beyond Cycle 1 will be discontinued from study medication. In cases where progression is not clear and, in the opinion of the investigator, the participant may be having clinical benefit, the participant may continue treatment, but must be reimaged within 2 cycles of treatment.
4. The participant, for any reason, requires treatment with another therapeutic agent or modality for his/her cancer (with the exception of palliative bone-directed radiotherapy). In this case, discontinuation from the study treatment must occur before introduction of the new agent or modality.

---

5. Participant takes prohibited concomitant medications as defined in this protocol.

Participants who discontinue the study medication and/or study early will have end-of-study (SFU) procedures performed as shown in the Schedules of Activities for Part A ([Table 1-4](#)), Part A1 ([Table 1-5](#) and [Table 1-6](#)), Part B ([Table 1-7](#)), and Part C ([Table 1-8](#)).

See the Schedules of Activities for Part A ([Table 1-4](#)), Part A1 ([Table 1-5 and Table 1-6](#)), Part B ([Table 1-7](#)), and Part C ([Table 1-8](#)) for data to be collected at the time of study treatment discontinuation and follow-up and for any further evaluations that need to be completed.

#### **7.1.4        Temporary discontinuation of study medication**

A treatment dose may be withheld if a participant experiences toxicity as described in Section [6.6.1.2](#) (Part A), Section [6.6.1.3](#) Part A1), Section [6.6.2.2](#) (Part B), and Section [6.6.3.1](#) (Part C).

Participants who fail to receive the second planned dose of UCB6114 within 7 days of the scheduled administration day during the DLT Observation Period for reasons not related to toxicity will be replaced by a new participant in that cohort.

Treatment with UCB6114 may temporarily be suspended for up to 3 weeks beyond the scheduled treatment day until toxicities are resolved to CTCAE Grade 2 or less. If UCB6114 is held for more than 3 weeks beyond the scheduled treatment day, then the participant will be discontinued from treatment and will be followed up for safety per schedule of assessment.

#### **7.2        Participant discontinuation/withdrawal from the study**

The criteria for enrollment must be followed explicitly. A Treatment Allocation/Enrolment Plan and management process (IVRS) may be utilized to ensure strict compliance.

Participants are free to withdraw from the study at any time, without prejudice to their continued care.

A participant may withdraw from the study at any time at his/her own request, or may be withdrawn at any time at the discretion of the investigator for safety or compliance reasons.

Participants should be withdrawn from the study if any of the following events occur:

1. Participant withdraws his/her consent.
2. Participant develops an illness or comorbidity that would interfere with his/her continued participation.
3. The investigator considers it in the best interest of the participant to be withdrawn. If this decision is made because of an SAE or a clinically significant laboratory value, then appropriate supportive measures are to be taken. UCB or its designee is to be alerted immediately.
4. Participant is noncompliant with the study visit schedule.

If the participant withdraws consent for disclosure of future information, the Sponsor may retain and continue to use any data collected before such a withdrawal of consent.

If a participant withdraws from the study, he/she may request destruction of any samples taken and not tested, and the investigator must document this in the site study records.

---

If any participant withdraws/is withdrawn from the study, the site will attempt to contact the participant and facilitate completion of the SFU Visit and the Final Visit. However, participants will not be followed up if they have withdrawn their consent to do so.

The primary reason for withdrawal from the study should be documented on the appropriate eCRF page.

Investigators should inform the study physician or medically qualified designee in the event that a participant is withdrawn from the study.

Participants who withdraw from the study before receiving study medication will be replaced.

### **7.3 Lost to follow up**

A participant will be considered lost to follow-up if he or she repeatedly fails to return for an SFU and is unable to be contacted by the study site.

The following actions must be taken if a participant fails to return to the clinic for a required study visit:

- The site must attempt to contact the participant and reschedule the missed visit as soon as possible and counsel the participant on the importance of maintaining the assigned visit schedule and ascertain whether or not the participant wishes to and/or should continue in the study.
- Before a participant is deemed lost to follow-up, the investigator, study physician, or medically qualified designee must make every effort to regain contact with the participant (at least 1 phone call and 1 written message to the participant), and document his/her effort (date and summary of the phone call and copy of the written message in the source documents), to complete the final evaluation. All results of these evaluations and observations, together with a narrative description of the reason(s) for removing the participant, must be recorded in the source documents. The eCRF must document the primary reason for withdrawal.

Should the participant continue to be unreachable, he/she will be considered to have withdrawn from the study with a primary reason of lost to follow-up documented in the eCRF.

### **7.4 COVID-19 Pandemic**

In the context of the COVID-19 pandemic, investigators should have individualized benefit-risk discussions with study participants during Screening and the course of the study. Such discussions should take into consideration the ongoing assessment of the study participant's medical status as well as the COVID-19 pandemic status in the geographic region. Investigators must elicit from the participant any suspected or known exposure to COVID-19 or a confirmed COVID-19 positive diagnosis. To accommodate potential COVID-19 restrictions, the study procedures may be adapted. Such adaptations may include replacing in-clinic visits with video consultations, flexibility in the timing and/or location of assessment collection, and any other changes deemed necessary until such restrictions are lifted. Clinical sites may arrange for virtual study visits or home visits to continue collection of safety and PK data. Participants who miss doses due to a positive COVID-19 diagnosis or a known exposure may continue in the study if, in the opinion of the investigator, they are experiencing clinical benefit and it is in their best interest to continue treatment. A study participant may resume treatment after missing doses due to COVID-19 pandemic restrictions, exposure, or infection provided that the protocol-defined

study drug discontinuation criteria are not met. In such cases, the investigator should assess all available medical information prior to re-initiating dosing. In the event of a temporary dosing stop due to COVID-19, participants who were enrolled prior to stop may receive home or virtual visits to continue collection of safety and PK data. Adverse events associated with COVID-19 are discussed in Section 9.2.

Any changes to the study to manage the impact of COVID-19 will be communicated to the regulatory authorities according to local guidance.

## 8 STUDY AND SITE DISCONTINUATION

The investigator or UCB have the right to stop or terminate the study at any time, for any ethical, medical, or scientific reason, while considering the rights, safety, and well-being of the participant(s).

Study site participation may be discontinued if UCB, the investigator, the IRB/ethical review board, or the regulatory authority deems it necessary for any scientific, medical, or ethical reason. The study will be discontinued if UCB, while considering the rights, safety, and wellbeing of the participant(s), deems it necessary for any scientific, medical, or ethical reason.

## 9 STUDY ASSESSMENTS AND PROCEDURES

Study procedures and their timing are summarized in the Schedules of Activities for Part A ([Table 1-4](#)), Part A1 ([Table 1-5](#) and [Table 1-6](#)), Part B ([Table 1-7](#)), and Part C ([Table 1-8](#)). Study procedures and their timing for modules subsequent to Parts A, A1, B, and C will be described in a planned protocol amendment.

Protocol waivers or exemptions are not allowed.

Immediate safety concerns should be discussed with the Sponsor immediately upon occurrence or awareness to determine if the participant should continue or discontinue study treatment.

Adherence to the study design requirements, including those specified in the Schedules of Activities for Part A ([Table 1-4](#)), Part A1 ([Table 1-5](#) and [Table 1-6](#)), Part B ([Table 1-7](#)), and Part C ([Table 1-8](#)), is essential and required for study conduct.

All Screening evaluations must be completed and reviewed to confirm that potential participants meet all eligibility criteria. The investigator will maintain a Screening log to record details of all participants screened and to confirm eligibility or record reasons for Screening failure, as applicable.

Procedures conducted as part of the participant's routine clinical management (eg, blood count) and obtained before signing of the ICF may be utilized for Screening or baseline purposes provided the procedures met the protocol-specified criteria and were performed within the time frame defined in the Schedules of Activities for Part A ([Table 1-4](#)), Part A1 ([Table 1-5](#) and [Table 1-6](#)), Part B ([Table 1-7](#)), or Part C ([Table 1-8](#)), as applicable.

In **Part A**, the maximum amount of blood collected from each participant during Screening will be approximately 8 to 10mL. In the case of liver function abnormalities considered potential Hy's Law cases where the liver-specific ALP must be separated from the total ALP in participants with bone metastases, an additional volume of 2mL of blood will be collected.

The maximum amount of blood collected from each participant over the duration of Cycle 1 of Part A are indicated in [Table 9-1](#).

**Table 9-1: Total blood volume collected during Cycle 1 of Part A**

Sample	Number of samples	Volume of sample	Total blood volume
Hematology	4	<2mL	8mL
Biochemistry	4	<2mL	8mL
Coagulation	2	<2mL	4mL
Pregnancy (if applicable) a	1	2mL	2mL
<hr/>			
Pharmacodynamics (PD)	12	various (2.5 to 20mL)	83.5mL
Immunogenicity (ADA)	3	5mL	15mL
Total	38	-	180.5mL

ADA=antidrug antibody

Note: Repeat or unscheduled samples may be taken in addition, for safety reasons or for technical issues with the samples.

a This volume could be increased by 2mL per visit if serum pregnancy test is performed instead of urine for second pregnancy assessment during this cycle.

The maximum amount of blood collected from each participant during Cycle 2 of Part A will be approximately 82.5mL. This volume could be increased by up to 4mL if serum pregnancy test is performed instead of urine pregnancy test.

The maximum amount of blood collected from each participant during Cycle 3 of Part A will be approximately 72.5mL, and the maximum amount of blood collected from each participant from Cycle 4 onwards will be approximately 52.5mL. This volume could be increased by up to 4mL per cycle if serum pregnancy test is performed instead of urine pregnancy test

The maximum amount of blood collected from each participant during the SFU of Part A will be approximately 51.5mL.

In **Part A1**,

- The maximum amount of blood collected from each participant during **Screening** will be approximately 42 to 44mL (if pregnancy test is applicable). In the case of liver function abnormalities considered potential Hy's Law cases where the liver-specific ALP must be separated from the total ALP in participants with bone metastases, an additional volume of 2mL of blood will be collected.
- The maximum amount of blood collected from each participant over the duration of **Cycle 1** is indicated in [Table 9-2](#).
- The maximum amount of blood collected from each participant during **Cycle 2** will be approximately 51.5mL for Cohorts 1, 2 and 4, and 47.5mL for Cohort 3. This volume could be increased by up to 2mL if serum pregnancy test is performed instead of urine pregnancy test.

- The maximum amount of blood collected from each participant during **Cycle 3** will be approximately 60.5mL for Cohorts 1 and 2, and 56.5mL for Cohorts 3 and 4. This volume could be increased by up to 2mL per cycle if serum pregnancy test is performed instead of urine pregnancy test. If the on-treatment biopsy is not performed an additional volume of up to 9mL could be collected for additional PK and circulating Gremlin-1 assessment.
- The maximum amount of blood collected from each participant from **Cycle 4 onwards** will be approximately 46.5mL for Cohorts 1 and 2, and 42.5mL for Cohorts 3 and 4. This volume will be increased by up to 7mL (2mL per cycle if serum pregnancy test is performed instead of urine pregnancy test and 5mL every third cycle [Cycle 6, Cycle 9] for immunogenicity).
- The maximum amount of blood collected from each participant during the SFU Visit will be approximately 47.5mL.

**Table 9-2: Total blood volume collected during Cycle 1 of Part A1**

Sample	Cohorts	Volume of sample	Cohorts 1, 2, 4		Cohort 3	
			Nº of samples	Total blood volume	Nº of samples	Total blood volume
Hematology		<2mL	2	<4mL	1	<2mL
Biochemistry		<2mL	2	<4mL	1	<2mL
Coagulation		<2mL	1	2mL	1	2mL
Pregnancy (if applicable) a		2mL	1	2mL	1	2mL
PD		various (2.5 to 20mL)	7	43.5mL	4	16mL
Immunogenicity (ADA)		5mL	1	5mL	1	5mL
Total		-	-	80.5mL	-	49mL

ADA=antidrug antibody; Nº=number; PD=pharmacodynamics; PK=pharmacokinetics

a This volume could be increased by 2mL per visit if serum pregnancy test is performed instead of urine for second pregnancy assessment during this cycle.

Note: Repeat or unscheduled samples may be taken in addition, for safety reasons or for technical issues with the samples.

In **Parts B and C**, the maximum amount of blood collected from each participant during Screening will be approximately 38.5mL. In the case of liver function abnormalities considered potential Hy's Law cases where the liver-specific ALP must be separated from the total ALP in participants with bone metastases, an additional volume of 2mL of blood will be collected.

The maximum amount of blood collected from each participant over the duration of Cycle 1 of Parts B and C is indicated in **Table 9-3**.

**Table 9-3: Total blood volume collected during Cycle 1 of Parts B and C**

Sample	Number of samples	Volume of sample	Total blood volume
Hematology	4	<2mL	8mL
Biochemistry	4	<2mL	8mL
Coagulation	2	<2mL	4mL
Pharmacodynamics (PD)	4	various (4 to 20mL)	32mL
Immunogenicity (ADA)	1	5mL	5mL
Total	19	-	77mL a

Note: Repeat or unscheduled samples may be taken in addition, for safety reasons or for technical issues with the samples.

a This volume could be increased by 2mL per visit at which serum pregnancy test is performed

The maximum amount of blood collected from each participant during Cycle 2 will be approximately 101mL. This volume could be increased by up to 2mL if serum pregnancy test is performed instead of urine pregnancy test.

The maximum amount of blood collected from each participant during subsequent cycles and the SFU will be approximately 44mL. This volume could be increased by up to 2mL per cycle if serum pregnancy test is performed instead of urine pregnancy test.

## 9.1 Safety assessments

Planned time points for all safety assessments are provided in the Schedules of Activities for Part A ([Table 1-4](#)), Part A1 ([Table 1-5](#) and [Table 1-6](#)), Part B ([Table 1-7](#)), and Part C ([Table 1-8](#)). Safety assessments for Parts A1, D, E, F, and G will be described in a protocol amendment.

### 9.1.1 Physical examination

The investigator or other designated clinician will perform a complete physical examination at Screening and on Cycle 1 Day 1 predose (Part A, Part A1 and Part C) or within 3 days prior to administration of any IMP (Part B). Physical examination will be symptom-directed at all other visits.

A complete physical examination will include, at a minimum, head, eyes, ears, nose, and throat; general abdomen; lymph nodes; and cardiovascular, respiratory, gastrointestinal, neurological, musculoskeletal, hepatic, and genitourinary (as clinically indicated) systems. Weight will also be measured and recorded. Height will only be recorded at Screening.

Signs and symptoms of concomitant disease and/or conditions should also be assessed. Investigators should pay special attention to clinical signs related to previous serious illnesses.

Clinically relevant findings or worsening of previous findings will be recorded in the eCRF as an AE.

### **9.1.2 Vital signs**

Vital signs will be measured in a semi-supine position after 5 minutes rest and will include temperature, systolic and diastolic blood pressure, pulse, and respiration rate. Vital sign measurements should be recorded prior to collection of PK samples.

### **9.1.3 Electrocardiograms**

TriPLICATE 12-lead ECG will be obtained using an ECG machine that automatically calculates the heart rate and measures PR, QRS, and QT intervals. Refer to Section [7.1.2](#) for QTc withdrawal criteria and any additional QTc readings that may be necessary.

All ECG recordings should be taken with the study participant resting in the supine position for at least 5 minutes before the recording. When coinciding with blood sample draws for PK, ECG assessment should be performed prior to blood sample collection, such that the blood sample is collected at the nominal time.

The 3 ECG tracings should be obtained as closely as possible in succession, within 2 to 10 minutes at each time point.

All ECGs will be evaluated for any clinically relevant changes by the investigator.

Electrocardiograms may be collected for central reading. During the visit, the assessment of the ECG by the investigator or designee will be used to determine eligibility and continuation in the study.

### **9.1.4 Echocardiograms**

Echocardiograms will be collected from all participants according to the Schedules of Activities for Part A ([Table 1-4](#)), Part A1 ([Table 1-5](#) and [Table 1-6](#)), Part B ([Table 1-7](#)), and Part C ([Table 1-8](#)). Left ventricular ejection fraction will be measured and recorded in the eCRF expressed as a percentage.

### **9.1.5 Clinical safety laboratory assessments**

Hematology, blood chemistry, coagulation, and urinalysis will be collected at the time points described in the Schedules of Activities for Part A ([Table 1-4](#)), Part A1 ([Table 1-5](#) and [Table 1-6](#)), Part B ([Table 1-7](#)), and Part C ([Table 1-8](#)) and analyzed at a local laboratory. See Appendix 2 (Section [11.2](#)) for the list of clinical laboratory tests to be performed.

The investigator must review the laboratory report, document this review, and record any clinically relevant changes occurring during the study in the AE section of the eCRF. The laboratory reports must be filed with the source documents. Clinically significant abnormal laboratory findings are those which are not associated with the underlying disease, unless judged by the investigator to be more severe than expected for the participant's condition.

Chemistry, hematology, and coagulation (where applicable) results should be available for review prior to infusion of treatment.

All laboratory tests with values considered clinically significantly abnormal during participation in the study or within 24 hours after the final dose of study medication should be repeated until the values return to normal or baseline or are no longer considered clinically significant by the investigator or study physician or medically qualified designee.

If such values do not return to normal/baseline within a period of time judged reasonable by the investigator, the etiology should be identified and the Sponsor notified.

All protocol-required laboratory assessments, as defined in Appendix 2 (Section 11.2), must be conducted in accordance with the laboratory manual and the Schedules of Activities for Part A (Table 1-4), Part A1 (Table 1-5 and Table 1-6), Part B (Table 1-7), and Part C (Table 1-8).

If laboratory values from nonprotocol-specified laboratory assessments performed at the institution's local laboratory require a change in participant management or are considered clinically significant by the investigator (eg, SAE or AE or dose modification), then the results must be recorded in the eCRF.

### **9.1.6        Pregnancy testing**

Procedures for pregnancy testing and contraceptive use are provided in Appendix 4 (Section 11.4). Pregnancy testing should be collected as described in the Schedules of Activities for Part A (Table 1-4), Part A1 (Table 1-5 and Table 1-6), Part B (Table 1-7), and Part C (Table 1-8).

For female participants of childbearing potential, a serum pregnancy test with sensitivity of at least 25mIU/mL will be performed on 2 occasions prior to starting study therapy, as follows: once at the start of Screening and once at the Day 1 Cycle 1 visit immediately before the investigational product administration.

Following a negative pregnancy test result at Screening, appropriate contraception must be commenced, and another negative pregnancy test result will then be required at the Day 1 Cycle 1 Visit before the participant may receive the study treatment.

Serum or urine pregnancy tests will also be routinely repeated twice at every treatment cycle during the active Treatment Period, at the Final Visit, and additionally whenever 1 menstrual cycle is missed or when potential pregnancy is otherwise suspected. In the case of a positive pregnancy test, the participant will be withdrawn from treatment but may remain in the study (Section 9.2.5).

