c From Cycle 3 and Cycle 4 onwards, visits on Day 22 may be omitted at the discretion of the investigator and based on toxicity seen at Cycle 1 and 2, unless these visits were required for tumor assessments, or participant assessment.

d The following safety assessments will be performed predose: physical examination, vital signs, hematology, blood chemistry, coagulation, urinalysis, pregnancy testing, ECOG performance status, echocardiograms, and ECG. All other safety assessments will be performed postdose.

e The visit on Day 22 may take place at any point from Day 21 to Day 28 of Cycle 2; tumor assessments should take place within this window at the investigator's discretion.

f When participants are unable to attend the SFU or Final Visit, it will not be considered a protocol deviation.

g Informed consent must be given before any study-specific Screening procedures are performed.

h ECGs are to be performed in triplicate with the participant in a supine position after a minimum of 5 min rest. When ECG coincides with PK (and PD), the ECG should be performed first. On Days 1 and 15 of Cycle 1, triplicate ECGs should be performed 3 times: the first predose; the second at the end of the infusion; and the third 8 hours after the end of the infusion. For all other cycles, triplicate ECGs should be performed predose.

i Pregnancy tests measure serum or urine  $\beta$ -hCG. Serum tests should be performed at Screening and visit immediately before the investigational product administration on Day 1 Cycle 1. Serum or urine pregnancy tests must be performed prior to dosing on dosing days. Additional pregnancy tests should also be performed during the study if indicated.

[figure not shown]
j UCB6114 is administered as an iv infusion on Days 1 and 15 of each cycle, until the occurrence of progressive disease, unacceptable toxicity, or withdrawal of consent.

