d Serum pregnancy test must be performed at screening. Serum or urine pregnancy test must be performed prior to dosing on Day 1 of each cycle. Additional pregnancy tests should also be performed during the study if indicated.

e A complete physical examination is to be performed at Screening and on Cycle 1 Day 1 prior to dosing with UCB6114. Physical examination will be symptom-directed and performed prior to administration of UCB6114 on all other visits.

f Assessments to be performed on dosing day only. Not applicable for Cohort 4.

g On treatment days, vital signs will be assessed at multiple time points in a semi-supine position after 5min of rest; prior to dosing, 10min ( $\pm$ 5min) and 30min ( $\pm$ 10min) after the start of the infusion, at the end of the infusion (+15min) and 2h after the end of the infusion (+15min). In addition, on Cycle 1 Day 1, vital signs will also be assessed at 5h (+2h) after the end of the infusion. Vital signs will be assessed prior to collection of PK samples.

h If there are abnormalities in urine dipstick, a microscopic analysis should be performed (including crystals). Urinalysis does not have to be repeated on Cycle 1 Day 1 predose if performed within 72h of starting dosing.

i Laboratory tests (hematology, blood chemistry, and coagulation) do not have to be repeated on Day 1 predose if performed within 72h of starting dosing. They may be obtained 24h prior to the scheduled visit and may be obtained at local laboratories.

j During the treatment period, echocardiograms are to be completed at the beginning of Cycle 3 ( $\pm$  7 days), as clinically indicated afterwards, and at the SFU Visit.

 Immunogenicity (ADA) samples will be collected on Cycle 1 Day 1, Cycle 2 Day 1, Cycle 3 Day 1, and Day 1 of every third cycle thereafter (i.e. cycle 6, 9 etc.) and at the SFU Visit.

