d Serum pregnancy test must be performed in Screening and does not have to be repeated on Day 1 predose if performed within 3 days prior to starting any IMP. If a serum pregnancy test was performed at Screening more than 3 days prior to starting any IMP, a urinary pregnancy test can be performed on Day 1 prior to dosing with any IMP. A serum or urinary test can be performed on all other visits.

e TFD/TPI can be dispensed once eligibility is confirmed (see footnote b).

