#### **4.1.4        Part B – Dose escalation with TFD/TPI**

Part B is a single arm open-label multiple ascending dose-escalation module of ONC001 evaluating UCB6114 in combination with TFD/TPI to identify the recommended Phase 2 dose of UCB6114 when used in combination with TFD/TPI (RP2D-T). Up to 27 participants with unresectable locally advanced or metastatic colorectal adenocarcinoma, gastric adenocarcinoma, or adenocarcinoma of the gastroesophageal junction will be enrolled.

Part B of ONC001 is planned to be initiated after Cohort 3 of Part A has completed the 28-day DLT assessment period and once the SMC has provided a recommendation to dose escalate to the next protocol-defined level in Part A of the study.

During the Treatment Period, UCB6114 will be administered in combination with TFD/TPI. UCB6114 will be administered as an iv infusion every 2 weeks (Q2W), while TFD/TPI will be administered orally twice daily (bid) within 1 hour of completion of morning and evening meals at home on Days 1 to 5 and Days 8 to 12 (28-day cycle). For the convenience of the participants, TFD/TPI can be administered at home to allow for the 12-hour interval between TFD/TPI doses associated with meals. For administration at home on Cycle 1 Day 1, eligibility must be confirmed within 3 days prior to Day 1 dosing as per the Schedule of Assessments.

Trifluridine/tipiracil will be administered at the recommended standard of care dose. The starting dose of UCB6114 in Part B will depend on the dose level evaluated in Cohort 3 of Part A (anticipated to be 500mg Q2W iv) and the emerging safety profile of UCB6114 monotherapy, including any overlapping toxicity with TFD/TPI.

Part B will be undertaken using the mTPI method. A target DLT rate of 25% with an equivalence interval (20% to 30%) will be used to estimate the MTD during dose escalation. For all dose levels, enrolled participants will be treated in cohorts of 2 to 4 participants (target of 3), who can

---

be treated in parallel. Each dose level may have more than one cohort and will have a minimum of 3 evaluable participants.

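### Section 9.1.6 sets one pregnancy-testing rule for all parts, but the Part A1 and Part B schedules require less, leaving the Day 15 infusion without a required test in Part A1 Cohorts 1 and 2 and in Part B

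*Protocol*

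**What the plan says.** Section 9.1.6 refers to the Schedules of Activities for Parts A, A1, B and C and then sets rules for every woman of childbearing potential, with no part singled out. A serum test is to be done at Screening and again at the Cycle 1 Day 1 visit, and "another negative pregnancy test result will then be required at the Day 1 Cycle 1 Visit before the participant may receive the study treatment". During treatment, "Serum or urine pregnancy tests will also be routinely repeated twice at every treatment cycle during the active Treatment Period".

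The part-specific schedules say:

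- **Part A (Table 1-4, footnote i):** "Serum tests should be performed at Screening and visit immediately before the investigational product administration on Day 1 Cycle 1", and "Serum or urine pregnancy tests must be performed prior to dosing on dosing days".
- **Part A1 (Table 1-5, footnote d; Table 1-6, footnote d is the same):** serum at Screening, then "Serum or urine pregnancy test must be performed prior to dosing on Day 1 of each cycle".
- **Part B (Table 1-7, footnote d):** "Serum pregnancy test must be performed in Screening and does not have to be repeated on Day 1 predose if performed within 3 days" before any IMP. Otherwise a urine test on Day 1 before dosing is accepted. For later visits, "A serum or urinary test can be performed on all other visits". The table row is marked on Day 1 only within each cycle.
- **Part C (Table 1-8, footnote d):** a serum or urine test on each dosing day, before any IMP.

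Appendix 4 (Section 11.4) says testing should be done at every visit in the treatment period.

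**The concern.** A site in Part A1 or Part B that follows its own schedule departs from the wording of Section 9.1.6 on frequency, and it may also depart on the type and timing of the test before first dose. Section 9 allows no waivers, and no order of precedence is stated.

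The practical consequence is the Day 15 infusion. A positive test stops treatment (Sections 7.1.3 and 9.1.6), so the test acts as a gate before dosing. In Part A1 Cohorts 1 and 2 and in Part B that gate is required before the Day 1 infusion but not before the Day 15 infusion. A pregnancy with no missed period and no other suspicion could pass Day 15 undetected. Part A1 Cohort 1 repeats the Part A Cohort 5 dosing schedule, yet it loses the Day 15 test that Part A requires, and no reason is given.

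**Working it through.** There is no sample size or power figure to reproduce. The check counts required tests over the first two treatment cycles.

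**Inputs**
- UCB6114 is infused on Days 1 and 15 in Part A, Part A1 Cohorts 1 and 2, Part B and Part C, and on Day 1 only in Cohorts 3 and 4 (Figure 1-3, Tables 1-4, 1-7 and 1-8).
- Part B visits in Cycles 1 and 2 fall on Days 1, 8, 15 and 22 (Table 1-7).
- Assumption: the Cycle 1 Day 1 test counts as one of that cycle's two, which is how Part A's schedule works.

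**Required tests over two cycles.** Section 9.1.6 asks for 2 × 2 = 4 in every part.

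| Part | Own schedule | UCB6114 infusions with no required test |
|---|---|---|
| A | 2 × 2 = 4 | 0 of 4 |
| A1 Cohorts 1 and 2 | 1 × 2 = 2 | 2 of 4 (both Day 15) |
| A1 Cohorts 3 and 4 | 1 × 2 = 2 | 0 of 2 |
| B | 1 × 2 = 2, or 1 if the Cycle 1 Day 1 test is waived | 2 of 4 (both Day 15) |
| C (footnote) | 2 × 2 = 4 | 0 of 4 |

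Where Part B uses its waiver, the first infusion is counted as covered by the serum test within the preceding 3 days.

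Under Appendix 4's every-visit wording the count would be 2 × 2 = 4 in Part A1 Cohorts 1 and 2, and 4 × 2 = 8 in Part B.

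**Source of the counts.** The Part B pregnancy row in Table 1-7 is complete: marks at both screening columns, Day 1 of Cycles 1 and 2, Day 1 from Cycle 3, SFU and Final Visit, and none on Days 8, 15 or 22. The Part A1 and Part C rows cannot be aligned in the text available, so those parts are counted from their footnotes, which are intact.

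**Test type on Cycle 1 Day 1.** Section 9.1.6: serum. Part A: serum. Parts A1 and C: serum or urine. Part B: urine allowed, or no test if serum was done within 3 days.

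**Planned participants in parts with the Day 15 gap.** Cohort 1 (8) + Cohort 2 (8) + Part B (27) = 43. This includes men and women not of childbearing potential.

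**Signs that Section 9.1.6 was not updated.** Section 9.1.1 gives Part B its own 3-day rule for the physical examination, but Section 9.1.6 has no such exception. Table 9-2, the Part A1 blood-volume table, mentions a second pregnancy assessment in Cycle 1 that the Part A1 schedules do not require.

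**The case against.** The strongest reply is that the Schedules govern. Section 9.1.6 itself sends sites to them, Section 9 makes adherence to them mandatory, and Section 9.1.5 requires the Appendix 2 laboratory tests, which include the hCG test, to follow them. On that reading the section is generic text that was not conformed to later parts. The Schedules do have the stronger claim, but this does not remove the conflict, because the same section goes on to fix a different test type and frequency in mandatory terms. Nor does it close the Day 15 gap, which comes from following the Schedules. Part B's permission to test at other visits is not a requirement.

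The safeguards also count: contraception is mandatory, and tests are required after a missed period or on suspicion. This is why the point is of low severity.

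Four stronger readings are tempting, and the Protocol does not support them.

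- *Only Part A agrees with Section 9.1.6.* Part C's footnote gives the same frequency; it differs only in allowing urine on Cycle 1 Day 1.
- *The three frequencies are all mandatory.* Appendix 4 is worded as a recommendation.
- *Part B sites cannot comply.* Section 4.1.4 says "For administration at home on Cycle 1 Day 1, eligibility must be confirmed within 3 days prior to Day 1 dosing", and Section 4.3.3.2.1 lets tablets be dispensed up to 3 days early. But home dosing is optional, and sites may do all assessments on Day 1 before any dose. The clash arises only when a home TFD/TPI dose precedes the Day 1 visit test.
- *The conflict affects 32 + 27 = 59 participants, all of Parts A1 and B.* That is not a sound count. Part A has visits without a scheduled test, so it also falls short of Appendix 4, and Part C's urine allowance departs from Section 9.1.6, so neither part is free of conflicting wording.

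**Conclusion.** The inconsistency stands in the current text. Section 9.1.6 requires two tests per cycle and a negative serum result at the Cycle 1 Day 1 visit in all parts. The Part A1 and Part B schedules require one serum-or-urine test per cycle, and Part B can waive the Cycle 1 Day 1 test. Part B's serum-within-3-days rule is a reasonable gate in itself; the fault is that Section 9.1.6 does not allow for it.

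The material part is the missing Day 15 requirement in Part A1 Cohorts 1 and 2 and in Part B. The number of women of childbearing potential among the 43 planned participants is not given, so no participant-level effect can be stated. Cohorts 3 and 4 fall short of two tests per cycle but have a test before every infusion. The point concerns safety procedure and site compliance, is of low severity, and touches no endpoint, DLT rule or dose-escalation decision.

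**What to change.** 1. In Tables 1-5 and 1-7 and their footnotes d, add a serum or urine test before the Day 15 UCB6114 infusion for Part A1 Cohorts 1 and 2 and for Part B. Cohort 4 needs none on Day 15. Keep Part B's existing Cycle 1 Day 1 waiver.
2. In Section 9.1.6, replace the twice-per-cycle requirement with a test before each UCB6114 infusion as the Schedule of Activities sets out.
3. In Section 9.1.6, make the pre-first-dose rule part-specific:
   - Part A: serum at Screening and on Cycle 1 Day 1.
   - Parts A1 and C: serum at Screening, and serum or urine on Cycle 1 Day 1.
   - Part B: a negative serum test within 3 days before any IMP, or otherwise a negative urine test on Day 1 before any IMP, including any TFD/TPI dose taken at home.
4. Align Appendix 4's every-visit wording with the Schedules.

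The cost is protocol wording plus one extra test per cycle, which can be urine, for women of childbearing potential at a Day 15 dosing visit that already exists. If serum is used instead, it adds 2 mL of blood, the volume given in Section 9.
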